5.1.7 Pregnancy test

A pregnancy test (urine or serum) will be collected during pretreatment period and within 7 days of study treatment start. It will be repeated every Odd Cycle if female patient of child-bearing potential remains on study.

5.1.8 Electrocardiogram (ECG)

ECG assessments will be performed with standard 12-lead ECG equipment according to standard procedures. Pre-treatment ECGs should be performed after vital signs are

obtained and before any blood draws. Abnormalities in the ECG that lead to a change in subject management (e.g., dose reduced or withheld, requirement for additional medication or monitoring) or result in clinical signs and symptoms are considered clinically significant for the purposes of this study and will be recorded on the AE CRF. If values meet criteria defining them as serious, they must be reported as SAEs). When an ECG time point coincides with other activities, the ECG will be collected first, followed by vital signs.

5.1.9 Archival tumor tissue (optional)

Adequate archival frozen or fixed tissue available from primary or metastatic site for genotypic analysis (at least 15 unstained slides and/or tumor block).

5.1.10 Whole blood collection (optional)

Whole blood will be collected and banked for future correlative/exploratory analysis and will be obtained Cycle 1 Day 1 (-7 day window) and again +/- 5 days of Cycle 3 Day 1.

For each subject, the Pre-Treatment Period ends upon receipt of the first dose of study treatment or final determination that the subject is ineligible for the study.

5.2 Treatment Period

During the Treatment Period subjects will receive cabozantinib until either disease progression, the occurrence of unacceptable drug-related toxicity or for other reason(s) for subject withdrawal as described in Section 2.6. Subjects should be instructed to immediately inform the principal investigator (PI) of any AEs. Subjects experiencing dizziness, sleepiness, or other symptoms that could influence alertness or coordination should be advised not to drive or operate other heavy machinery.

The following schedule of assessments applies to all subjects (Table 5-1). More frequent assessments should be obtained if clinically indicated.

Table 5-1: Study Assessments

	Study Treatment Period 1 Cycle = 21 days			Post-Treatment Period
	Within 28 days before 1 st Dose of Study Treatment	Cycle 1 Day 1 (-7 day window)	Day 1 of each subsequent Cycle (± 5 days)	30 - 37 Days after last dose
Informed consent	X			
Demographics	X			
Medical and cancer history/demographics	X			
Physical examination	X	X	X	X
Height	X			
Weight	X	X	X	X
Vital signs	X	X	X	X
ECOG performance status	X	X	X	X
Hematology (CBC w diff and platelets)	X	X	X	X
Chemistry (CMP, magnesium, LDH, phosphorus)	X	X	X	X
Amylase/Lipase	X	X	X	X
GGT		X		
Urinalysis and UPCR	X		X	X
PT/INR, PTT	X		X ¹	
TFTs (TSH, free T3, free T4)	X		X ¹	
12-lead ECG	X ²		X ¹	X
Cabozantinib administration		X (daily)	X (daily)	
Pregnancy test	X	X	X ¹	X
Tumor assessment ³	X		X (every 6 weeks for first 12 weeks, then every 9 weeks)	
CEA	X		X (every 3 weeks)	
Archival tumor tissue	X ³			
Whole blood collection for correlative analysis		X ⁴	(Cycle 3 Day 1) ⁴	
Concomitant medications	X		X	X
Adverse events	Continuous			X
Interim analysis			X ⁵	
Follow-up/EOS				X ⁶

ECG, electrocardiogram; ECOG, Eastern Cooperative Oncology Group; PT/INR, prothrombin time/International Normalized Ratio; PTT, partial prothrombin time, TFT, thyroid function test; UPCR, urine protein/urine creatinine ratio; EOS end-of-study

¹Odd cycle assessments

© 2017 AGICC/Criterion Inc.

PROPRIETARY & CONFIDENTIAL

Template Final Ver. 25OCT2017

Protocol 17CRC01/EXELIXIS IST56/Version 2.0 10/27/18

²ECG done in triplicate to assess average QTc for screening

³All sites of known disease must be assessed

⁴Adequate archival frozen or fixed tissue available from primary or metastatic site for genotypic analysis (at least 15 unstained slides and/or tumor block): Whole blood for correlative/exploratory analysis will be obtained Cycle 1 Day 1 (-7 day window) and Cycle 3 Day 1 (+/- 5 days)

⁵Upon enrolling the 16th patient, an interim analysis will be performed to evaluate PFS once 3 patients have met the 12 week PFS mark. An additional safety DMSC review will occur once 16 patients have been dosed through 12 weeks.

⁶Patients will be followed for up to 12 months to record their health and disease status after EOS assessment

If the subject is unable to have a study assessment taken within the defined time window due to an event outside of his or her control (e.g., clinic closure, personal emergency, inclement weather, vacation), the assessment should be performed as close as possible to the required schedule.

Regular tumor assessments should be performed in accordance to the guidelines in Section 5.5 to determine if PD is present.

The Treatment Period ends when a subject receives his or her last dose of study treatment; the subject then enters the Post-Treatment Period.

5.3 Post-Treatment Period

Subjects will return to the study site 30 to 37 days after their last dose of cabozantinib to complete end-of-study (EOS) assessments.

Laboratory and physical examinations will be performed. Remaining study treatment will be returned by the subject, and treatment compliance will be documented. Additional follow-up will occur for subjects with AEs related to study treatment that are ongoing at the time of this visit, and for subjects with SAEs related to study treatment that occur after the time of this visit.

Additional follow-up to record health and disease status will be done for up to 12 months after EOS. Survival information can be collected via telephone and should occur every 90 days (+/- 30 days) up to 12 months after EOS.

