- i. Active peptic ulcer disease, inflammatory bowel disease (eg, Crohn's disease), diverticulitis, cholecystitis, symptomatic cholangitis or appendicitis, acute pancreatitis or acute obstruction of the pancreatic duct or common bile duct, or gastric outlet obstruction
 - ii. Abdominal fistula, GI perforation, bowel obstruction, intra-abdominal abscess within 6 months before randomization,
- Note: Complete healing of an intra-abdominal abscess must be confirmed prior to randomization
- c. Other clinically significant disorders that would preclude safe study participation;

14. Major surgery within 12 weeks before the first dose of study treatment. Complete wound healing from major surgery and/or radiation must have occurred 1 month before the first dose of study treatment. Minor surgery (including uncomplicated tooth extractions) within 28 days before the first dose of study treatment with complete wound healing at least 10 days before the first dose of study treatment. Subjects with clinically relevant ongoing complications from prior surgery are not eligible;

15. QTcF > 500 msec within 1 month before the first dose of study treatment:

- a. Three ECGs must be performed for eligibility determination. If the average of these three consecutive results for QTcF is ≤ 500 msec, the subject meets eligibility in this regard.

16. Pregnant or lactating females;
17. Inability to swallow intact tablets;
18. Previously identified allergy or hypersensitivity to components of the study treatment formulations;
19. Diagnosis of another malignancy within 2 years before the first dose of study treatment, except for superficial skin cancers, or localized, low grade tumors deemed cured and not treated with systemic therapy;

ESTIMATED LENGTH OF SUBJECT PARTICIPATION

Subjects may continue to receive study treatment until they experience unacceptable drug-related toxicity or disease progression. Sponsor or investigator may terminate the study at any time.

ESTIMATED STUDY DATES

First quarter of 2018 to First quarter of 2020 (last study follow-up visit).

INVESTIGATIONAL REGIMEN DOSE/ROUTE/DURATION

Cabozantinib is supplied as 20-mg and administered orally at a dose of 60 mg/day.

SAFETY ASSESSMENTS

Safety will be monitored on an ongoing basis. Laboratory testing (chemistry, hematology tests) and urinalysis will be performed every 3 weeks. Other safety evaluations including EKGs will be performed every 6 weeks.

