7.3 Sample Size

The stage I sample size will consist of 16 subjects for interim analysis, then an additional 28 subjects for stage II for a total of 44 subjects.

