7.3.1 Sample Size Justification

Based on the phase III CORRECT trial investigating regorafenib versus best supportive care, the median PFS for patients with refractory colorectal cancer was 1.7 months in the placebo arm. Therefore, the PFS at 12 weeks would be approximately 13%, which will serve as the response rate in the null hypothesis. We have designed the trial to have at least 90% power to detect an improvement in the 12-week PFS rate of at least 20%, therefore the alternative hypothesis is that the 12-week PFS rate is 33%. The optimal design providing at least 90% power to detect the alternative while controlling the type I error rate at 0.05 uses at most 44 patients. This design has an actual type I error rate of 0.0441 (i.e. if the true 12-week PFS rate is less than or equal to 0.13, there is only a 4.4% probability of concluding that the PFS rate is greater than or equal to 0.33). This design has power of 0.906 to detect the alternative hypothesized 12-week PFS rate of 0.33. This trial design uses an average of 25.7 patients.

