8.1.2.2 Overall Survival (OS)

Overall survival will be defined as the time from administration of the initial dose of cabozantinib until death from any cause. PFS is defined above. Kaplan-Meier estimates of overall survival and progression-free survival rates will be calculated along with their corresponding 95% confidence interval.

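### Survival contact ends 12 months after each patient's own end-of-study visit, so beyond about 12 months the OS curve loses living early stoppers first and may read slightly high

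*Combined protocol and SAP*

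**What the plan says.** Section 5.2 sets how long treatment lasts: "During the Treatment Period subjects will receive cabozantinib until either disease progression, the occurrence of unacceptable drug-related toxicity", or another withdrawal reason listed in section 2.6. Section 5.3 then fixes the EOS visit: "Subjects will return to the study site 30 to 37 days after their last dose of cabozantinib to complete end-of-study (EOS) assessments". From that visit, "Survival information can be collected via telephone and should occur every 90 days (+/- 30 days) up to 12 months after EOS". Footnote 6 of Table 5-1 repeats the 12-month limit.

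Section 8.1.2.2 defines the endpoint ("Overall survival will be defined as the time from administration of the initial dose of cabozantinib until death from any cause") and the analysis ("Kaplan-Meier estimates of overall survival and progression-free survival rates will be calculated along with their corresponding 95% confidence interval"). Neither that section nor the Statistical Methods part of the Synopsis gives an OS censoring rule, a common cut-off date, a landmark time or a minimum number at risk.

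The Synopsis dates the study "First quarter of 2018 to First quarter of 2020 (last study follow-up visit". That calendar limit applies to every patient. On size, section 7.3 plans 16 patients in the first stage and 28 more in the second, 44 in all.

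**The concern.** Kaplan-Meier estimation needs censoring that is unrelated to prognosis. Here the censoring time is time on drug, plus about one month, plus 12 months. Time on drug is ended largely by progression. Among patients alive a year or more after first dose, those who stopped early are therefore the first to leave the risk set. If early stopping goes with shorter later survival, the patients who remain are favourably selected and the curve beyond that point is too high.

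Even without such a link, the rule gives up information. A patient who starts in Q1 2018 and stops after 2 months is no longer called after 2 + 1.1 + 12 = 15.1 months, around mid-2019, although the study's last follow-up is planned for Q1 2020.

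What is at stake is the late part of a secondary, descriptive curve and its confidence interval.

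**Working it through.** **The plan's own figures.** The plan states no OS median, event count or precision, so there is no OS figure to reproduce. Its two-stage design figures do reproduce. Summing over x = 3 to 16 the terms Bin(x; 16, p) × P(Bin(28, p) ≥ 10 − x) gives 0.0441 at p = 0.13 and 0.9055 at p = 0.33, with expected size 25.7 under the null. None of this uses OS.

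**When the rule can first censor.** As scheduled: time on drug + 30 to 37 days + 12 months, so not before about 13 months from first dose. If calls are counted from EOS, the fourth falls at 4 × 90 = 360 days. With the 30-day window it may fall at 330 days, about 11 months after EOS. Then 330 + 30 = 360 days, or 11.8 months plus time on drug. So 12 months is the safe limit.

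**Model for the tail (assumptions, because the documents give no OS data).** OS = P + Q, where P is time on drug and Q is survival after stopping. P has a 12-week rate of 33%, the plan's alternative. Q has a median of 6 months. The two are linked by a gamma frailty of variance v, with v = 0 meaning independence. Censoring is at P + 33.5 days + 12 months. The simulation used 400,000 patients per scenario. The standard error is √(S(1 − S)/44), with no censoring at all.

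| v | True 18-month OS | Kaplan-Meier | Bias (points) | SE (points) |
|---|---|---|---|---|
| 0 | 0.175 | 0.176 | 0 | 5.7 |
| 0.5 | 0.258 | 0.276 | 1.8 | 6.6 |
| 1 | 0.301 | 0.322 | 2.1 | 6.9 |

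The Kaplan-Meier estimate equals true survival at 12 and 13 months in every row. Median OS is about 8 to 9 months. If stopping is timed to the scans in section 5.5, the bias for v = 0.5 and 1 falls to about 1 to 1.5 points.

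**Separating the rule from the calendar (v = 0.5).** Without any calendar limit, 11.3 of 44 are alive at 18 months and 5.3 are still followed under the rule. With study end at E months and uniform accrual over A months (both assumed; Q1 2018 to Q1 2020 spans about 24 to 27 months), the share of patients with 18 months of calendar time is (E − 18)/A.

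| E / A | Share | Common cut-off: 11.3 × share | With the 12-month rule: 5.3 × share | Lost to calendar | Lost to rule |
|---|---|---|---|---|---|
| 24 / 18 | 0.33 | 3.8 | 1.8 | 7.5 | 2.0 |
| 24 / 12 | 0.50 | 5.7 | 2.7 | 5.6 | 3.0 |
| 27 / 12 | 0.75 | 8.5 | 4.0 | 2.8 | 4.5 |

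**Sensitivity to a different model.** Here PFS has a median of 1.7 months, borrowed from the plan's reference ("the median PFS for patients with refractory colorectal cancer was 1.7 months in the placebo arm"). OS is exponential with an assumed median of 6, 9 or 12 months, the PFS-OS correlation is 0.5, and E / A is 27 / 12. The 18-month estimate is 0.136, 0.272 and 0.382 under the rule, against 0.126, 0.251 and 0.355 with a common cut-off: 1.0, 2.1 and 2.7 points. Numbers at risk are 1.5, 2.5 and 3.1 against 4.1, 8.3 and 11.7, so the rule's own loss is larger when survival is longer. Without the calendar limit and with correlations of 0.5 to 0.8, the bias ranges over about 0.5 to 4 points. At zero correlation there is none, and nothing changes through 13 months.

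**The case against.** The strongest reply is that little depends on this. OS is secondary and single-arm, with no test, comparator or decision rule, and the plan promises no 18-month rate. The bias is well below the sampling error of 44 patients (16 if the trial stops at stage 1). Much of the thin tail comes from that size and from the calendar end, which censors late entrants however long they were treated. All of this stands, and it sets the priority.

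A reader might go further than the documents allow in three ways:

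- **That the whole OS curve, or its median, is distorted.** It is not. Deaths before about 12 months are captured whenever treatment stopped.
- **That the censoring is informative as a matter of fact.** The text establishes only that censoring depends on time on drug. Bias also needs a link between that time and later survival. Section 2.6 lets treatment end for toxicity, noncompliance or investigator judgement too, and the direction of those effects is unknown.
- **That a large error at 24 months follows.** Even with a common Q1 2020 cut-off, only about 0 to 2.7 of 44 patients would be at risk then in the scenarios above. The planned calendar barely observes that part of the curve.

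The reply does not answer the remaining point. The rule is written into the plan, it stops calls while the study is still open, and a common cut-off would keep the harmless calendar censoring while removing the part tied to treatment duration.

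**Conclusion.** The concern holds in limited form. Section 5.3 and Table 5-1 footnote 6 tie OS censoring to each patient's time on cabozantinib. OS estimates to about 12 months, a median below that, and the primary conclusion are not affected.

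Beyond 12 to 13 months, obtainable survival data are discarded. If earlier stopping predicts shorter later survival, the curve reads too high. Under the main assumptions (12-week PFS 33%, post-treatment median 6 months, frailty variance 0 to 1, accrual over 12 to 18 months, study end at 24 to 27 months), the 18-month bias is about 0 to 2 points against a standard error of about 6 to 7. The rule itself removes about 2 to 4.5 of 44 patients from the 18-month risk set. The rest of the loss is due to the study end date and the sample size. Other assumptions move these figures, as the sensitivity run shows, and the documents contain no OS data to choose between them. The priority is low.

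**What to change.** In section 5.3 and Table 5-1 footnote 6, collect survival status until death, withdrawal of consent, or one data cut-off date common to all patients, for example the planned last study follow-up. In section 8.1.2.2, state that patients not known to have died are censored at the earlier of last contact and that date, and show numbers at risk with the curve. The cost is protocol wording and a few extra telephone contacts with long survivors. It is best done before calls to early stoppers end, because the missing status may not be recoverable later.

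If follow-up is not extended, report Kaplan-Meier OS only to 12 months after first dose. Twelve months is safer than 13 because the call window allows a last contact about 11 months after EOS. The cost is that no later OS rate is reported.

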5.4 Laboratory Assessments

Laboratory panels are composed of the following:

Hematology		

 WBC count with differential (including at minimum: neutrophils, basophils, eosinophils, lymphocytes, monocytes) 	
 hematocrit platelet count RBC count hemoglobin 	
Serum chemistry		

 albumin ALP amylase ALT AST bicarbonate BUN chloride 	
 creatinine GGT (day 1 only) glucose (non-fasting permitted) ionized calcium or total and corrected calcium lactate dehydrogenase lipase 	
 magnesium phosphorus potassium sodium total bilirubin total protein
Urinalysis		

 appearance color pH specific gravity ketones protein UPCR 	
 glucose bilirubin nitrite creatinine urobilinogen 	
 occult blood (microscopic examination of sediment will be performed only if the results of the urinalysis dipstick evaluation are positive)
Other		

 TSH, Free T3 and T4 Pregnancy test (urine or serum) for women of child-bearing potential 		
 PT/INR or PTT 24-hour urine collection for protein

ALP, alkaline phosphatase; ALT, alanine aminotransferase; AST, aspartate aminotransferase; BUN, blood urea nitrogen; GGT, γ -glutamyltransferase; INR, International Normalized Ratio; PT, prothrombin time; PTT partial thromboplastin time; RBC, red blood cell; TSH, thyroid stimulating hormone; UPCR, urine protein/creatinine ratio; WBC, white blood cell.

Abnormalities in clinical laboratory tests that lead to a change in subject management (eg, dose delayed [withheld] or reduced, requirement for additional medication, treatment or monitoring)

are considered clinically significant for the purposes of this study, and will be recorded on the Adverse Events Case Report Form (CRF). If laboratory values constitute part of an event that meets criteria defining it as serious, the event (and associated laboratory values) must be reported as an SAE.

5.5 Tumor Assessment

For the purposes of this study, participants should be re-evaluated for response every 6 weeks for the first 12 weeks, followed by every 9 weeks thereafter.

Response and progression will be evaluated in this study using the new international criteria proposed by the RECISTv1.1 guideline [*Eur J Ca* 45:228-247, 2009]. Changes in the largest diameter (unidimensional measurement) of the tumor lesions and the shortest diameter in the case of malignant lymph nodes are used in the RECIST criteria.

All measurements should be taken and recorded in metric notation using a ruler, calipers, or a digital measurement tool. All baseline evaluations should be performed as closely as possible to the beginning of treatment and never more than 4 weeks before the beginning of the treatment.

The same method of assessment and the same technique should be used to characterize each identified and reported lesion at baseline and during follow-up. Imaging-based evaluation is preferred to evaluation by clinical examination unless the lesion(s) being followed cannot be imaged but are assessable by clinical exam.

Clinical lesions: Clinical lesions will only be considered measurable when they are superficial (*e.g.*, skin nodules and palpable lymph nodes) and ≥ 10 mm in diameter as assessed using calipers (*e.g.*, skin nodules). In the case of skin lesions, documentation by color photography, including a ruler to estimate the size of the lesion, is recommended.

Conventional CT and MRI: This guideline has defined measurability of lesions on CT scan based on the assumption that CT thickness is 5mm or less. If CT scans have slice thickness greater than 5 mm, the minimum size of a measurable lesion should be twice the slice thickness. MRI is also acceptable in certain situations (*e.g.* for body scans).

Use of MRI remains a complex issue. MRI has excellent contrast, spatial, and temporal resolution; however, there are many image acquisition variables involved in MRI, which greatly impact image quality, lesion conspicuity, and measurement. Furthermore, the availability of MRI is variable globally. As with CT, if an MRI is performed, the technical specifications of the scanning sequences used should be optimized for the evaluation of the type and site of disease. Furthermore, as with CT, the modality used at follow-up should be the same as was used at baseline and the lesions should be measured/assessed on the same pulse sequence. It is beyond

the scope of the RECIST guidelines to prescribe specific MRI pulse sequence parameters for all scanners, body parts, and diseases. Ideally, the same type of scanner should be used and the image acquisition protocol should be followed as closely as possible to prior scans. Body scans should be performed with breath-hold scanning techniques, if possible.

FDG-PET: While FDG-PET response assessments need additional study, it is sometimes reasonable to incorporate the use of FDG-PET scanning to complement CT scanning in assessment of progression (particularly possible 'new' disease). New lesions based on FDG-PET imaging can be identified according to the following algorithm:

- (a) Negative FDG-PET at baseline, with a positive FDG-PET at follow-up is a sign of PD based on a new lesion.
- (b) No FDG-PET at baseline and a positive FDG-PET at follow-up: If the positive FDG-PET at follow-up corresponds to a new site of disease confirmed by CT, this is PD. If the positive FDG-PET at follow-up is not confirmed as a new site of disease on CT, additional follow-up CT scans are needed to determine if there is truly progression occurring at that site (if so, the date of PD will be the date of the initial abnormal FDG-PET scan). If the positive FDG-PET at follow-up corresponds to a pre-existing site of disease on CT that is not progressing based on the anatomic images, this is not PD.
- (c) FDG-PET may be used to upgrade a response to a CR in a manner like a biopsy in cases where a residual radiographic abnormality is thought to represent fibrosis or scarring. The use of FDG-PET in this circumstance should be prospectively described in the protocol and supported by disease-specific medical literature for the indication. However, it must be acknowledged that both approaches may lead to false positive CR due to limitations of FDG-PET and biopsy resolution/sensitivity.

Note: A 'positive' FDG-PET scan lesion means one which is FDG avid with an uptake greater than twice that of the surrounding tissue on the attenuation corrected image.

PET-CT: At present, the low dose or attenuation correction CT portion of a combined PET-CT is not always of optimal diagnostic CT quality for use with RECIST measurements. However, if the site can document that the CT performed as part of a PET-CT is of identical diagnostic quality to a diagnostic CT (with IV and oral contrast), then the CT portion of the PET-CT can be used for RECIST measurements and can be used interchangeably with conventional CT in accurately measuring cancer lesions over time. Note, however, that the PET portion of the CT introduces additional data which may bias an Investigator if it is not routinely or serially performed.

Tumor markers: Tumor markers alone cannot be used to assess response. If markers are initially above the upper normal limit, they must normalize for a participant to be considered in complete clinical response.

